9.7.1.6.2 SECONDARY EFFICACY ANALYSES

Analyses for Key Secondary Efficacy Endpoints (revised per Amendment 05):

The key secondary analyses will be performed only if the primary analysis is significant. The treatment effect for elenbecestat 50 mg/day versus placebo, for each key secondary efficacy endpoint, will be tested using a sequential testing procedure at a significance level of 2-sided $\alpha = 0.05$, ie, any test will start only if the test with higher hierarchical order is significant.

The change from baseline in ADCOMS at 24 months will be analyzed using the same MMRM model as the primary efficacy analysis to compare elenbecestat 50 mg per day versus placebo on the FAS, using baseline ADCOMS in the model.

The change from baseline in amyloid PET SUVR at 24 months will be analyzed using the same MMRM model as the primary efficacy analysis to compare elenbecestat 50 mg per day versus placebo on the FAS, using baseline amyloid PET SUVR in the model. The same analysis will be performed within study as key secondary efficacy endpoint analyses.

Analyses for Other Secondary Endpoints (revised per Amendment 05)

The change from baseline in CDR-SB and ADCOMS at 24 months will be analyzed using the same MMRM model as the primary analysis for subjects enriched by baseline PET SUVR between e.g. 1.2 and 1.6 on the FAS.

The rate of change over time (mean slope) based on change from baseline in the CDR-SB will be analyzed using linear mixed effects (LME) models for multivariate normal data derived from a random coefficient model (slope analysis), where the mean slope in each group depends on a continuous assessment time. The LME model will include treatment group, baseline CDR-SB, randomization stratification variables, assessment time, baseline CDR-SB-by-assessment time, and treatment group-by-assessment time. ApoE4 status may be included in the model if appropriate.

Time to worsening of CDR scores by 24 months will be analyzed on the FAS using Cox regression model for treatment effect adjusting for randomization stratification factors. ApoE4 status may be included in the model if appropriate. (revised per Amendment 05) Time to worsening of a CDR score is defined as time from randomization to worsening of the CDR score (ie, the first worsening in 2 consecutive scheduled visits). For subjects whose CDR scores have not worsened by the end of the Treatment Period of the Core Study, the time to worsening of the CDR score will be censored at the date of last CDR assessment for these subjects.

Time to conversion to dementia for subjects who were not clinically staged as dementia at Baseline based on clinical diagnosis will be analyzed on the FAS using Cox regression model for treatment effect adjusting for randomization stratification factors. ApoE4 status may be included in the model if appropriate. (revised per Amendment 05) Proportion of subjects with dementia diagnosis at 24 months will be estimated using Kaplan—Meier method based on time to conversion to dementia based on clinical diagnosis. Time to conversion to dementia for subjects who were not clinically staged as dementia at Baseline based on clinical diagnosis is defined as time from randomization to conversion to dementia based on clinical diagnosis. For subjects without clinical dementia by the end of study, the time to conversion to dementia based on clinical diagnosis will be censored at the date of last dementia diagnosis.

The other continuous secondary efficacy endpoints as defined above will be analyzed using the same MMRM model as the primary efficacy analysis to compare elenbecestat 50 mg per day versus placebo on the FAS, using baseline value corresponding to the response variable in the model.

The relationship between clinical changes at 24 months (CDR-SB, ADCOMS, ADAS-cog14, MMSE, and FAQ) and changes in each of the biomarkers (amyloid PET, tau PET, CSF A β (1-x), t-tau, p-tau, vMRI, and fMRI) at 24 months, will be evaluated using an ANCOVA model. (revised per Amendments 03, 04, and 05) Changes in clinical scales at 24 months will be the response variables and either continuous or categorical change of biomarkers will be independent variables. The ANCOVA model will also include baseline value for clinical scale as a covariate, with treatment group and randomization stratification variables, as factors. ApoE4 status may be included in the model if appropriate. (revised per Amendment 05)

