8 STUDY OBJECTIVES

8.1 Primary Objective

The primary objective of the Core Study is:

- To determine whether elenbecestat is superior to placebo on the change from baseline in the Clinical Dementia Rating - Sum Of Boxes (CDR-SB) at 24 months in subjects with EAD pooled across studies E2609-G000-301 and E2609-G000-302 (revised per Amendment 05)

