9.7 Statistical Methods

All statistical analyses will be performed by the sponsor or designee. Statistical analyses will be performed using SAS software or other validated statistical software as required.

All statistical tests will be based on the 5% (2-sided) level of significance, unless specified.

For statistical methods specific to the Extension Phase, refer to [Appendix 5 in Section 12](#).

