9.7.1.6.1 PRIMARY EFFICACY ANALYSIS

The primary analysis will be based on an intent to treat philosophy without regard to adherence to treatment. The primary analysis of the change from baseline in CDR-SB at 24 months will be performed to compare elenbecestat 50 mg per day versus placebo using a linear mixed effects model for repeated measures (MMRM) on the FAS. The MMRM model will include fixed effects of treatment group, visit, treatment group by visit interaction, baseline CDR-SB, baseline CDR-SB by visit interaction, and randomization stratification variables (ie, region [7 levels], clinical dementia [yes, no], and concurrent AD medication use at randomization [Visit 2] [yes, no]). *ApoE4* status may be included in the model if appropriate. (revised per Amendment 05) An unstructured covariance matrix will be employed to model the covariance of within subject effect; if MMRM fails to converge then a covariance structure with fewer parameters from the following list will be employed according to the prespecified order in the list until the MMRM converges. The list of covariance structure will include Heterogeneous Toeplitz, Toeplitz, Heterogeneous Compound Symmetry, and Compound Symmetry. This primary analysis will include all observed post baseline data of the change from baseline in CDR-SB without imputation of missing values. The treatment effect for elenbecestat versus placebo will be compared at

24 months based on MMRM model. The LS means and difference in LS means between elenbecestat treatment group and placebo, and corresponding 95% CI will be presented.

The null hypothesis is that there is no difference in the mean change from baseline in CDR-SB at 24 months between elenbecestat 50 mg per day and placebo. The corresponding alternative hypothesis is that there is a difference in the mean change from baseline in CDR-SB at 24 months between elenbecestat 50 mg per day and placebo.

The primary analysis will be repeated to minimize the impact of change in concomitant AD medications where efficacy data after initiation of new AD medications and increase of current AD medications will be censored.

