9.7.1.7.3 PHARMACODYNAMIC, PHARMACOGENOMIC, AND OTHER BIOMARKER ANALYSES

The analysis of the biomarker endpoints defined as below will be performed to compare elenbecestat versus placebo using the appropriate prespecified statistical methods including MMRM model, ANCOVA, or non-parametric methods if the data is not normally distributed, etc. These analyses will be conducted without adjustment for multiplicity or sequential testing. For each endpoint, the treatment effect for elenbecestat 50 mg per day versus placebo will be tested at a significance level of 2-sided alpha = 0.05. (revised per Amendment 04)

- Change from baseline in tau PET signal at 24 months (revised per Amendment 04)
- Change from baseline in CSF biomarkers t-tau and p-tau at 24 months
- Change from baseline in CSF amyloid biomarkers $A\beta(1-42)$, and $A\beta(1-x)$ at 24 months (revised per Amendment 03)
- Change from baseline in total hippocampal volume at 12 and 24 months using vMRI
- Change from baseline in fMRI parameters as appropriate (revised per Amendment 05)
- Change from baseline in plasma amyloid biomarker (eg, $A\beta(1-x)$) at all assessments (revised per Amendment 05)
- Change from baseline in potential plasma and CSF biomarkers of AD (eg, NFL, VILIP1, YKL-40, and Ng) (revised per Amendment 05)

The relationship between exposure (in CSF, plasma) of elenbecestat with potential biomarkers of Alzheimer's disease as deemed appropriate will be evaluated using appropriate statistical model with the continuous changes in biomarker at 24 months as response variables and exposure variables (in CSF, plasma) of elenbecestat as independent variables.

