9.7.2 Determination of Sample Size

The sample size for this study is estimated for comparison of elenbecestat versus placebo with respect to a pooled analysis of studies E2609-G000-301 and E2609-G000-302 for the change from baseline in CDR-SB at 24 months. Based on the available data from the placebo group in Study BAN2401-G000-201 (a recently completed study with a comparable subject population), the mean and the standard deviation of the change from baseline in CDR-SB at 24 months in the placebo group are assumed to be 1.46 and 2.05, respectively, instead of 1.75 and 2.05, which are originally assumed by the available data from ADNI (of amyloid positive, MMSE equal or greater than 24, late MCI [global CDR=0.5, CDR memory box \geq 0.5]). Therefore, assuming a 25% reduction in the mean change from baseline CDR-SB at 24 months for elenbecestat compared to placebo with common standard deviation of 2.05 and 30% dropout rate, a total sample size of 1900 subjects, 950 subjects in each treatment group, will be required to detect the treatment difference between elenbecestat and placebo using a 2-sample t test with 90% power at a significance level of 2 sided alpha =0.05.

The pooled data from 2 studies (E2609-G000-301 and E2609-G000-302) will comprise the total sample size of approximately 1900 subjects. At least 850 subjects will be randomized in each study. (revised per Amendment 05)

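### The protocol makes performing the key secondary analyses, not only claiming significance, conditional on a significant primary, so a missed CDR-SB result leaves amyloid PET without a planned treatment estimate

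*Protocol*

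**What the plan says.** Protocol Section 9.7.1.6.2 opens its key secondary paragraph with "The key secondary analyses will be performed only if the primary analysis is significant". It then sets a fixed sequence at two-sided 0.05 in which "any test will start only if the test with higher hierarchical order is significant". The synopsis repeats both statements under its key secondary analyses. As listed in Section 9.7.1.1.2, the key secondary endpoints are ADCOMS (pooled), amyloid PET SUVR (pooled) and amyloid PET SUVR in the individual studies, all at 24 months.

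Other endpoints carry no such condition. Of the biomarker endpoints, Section 9.7.1.7.3 says: "These analyses will be conducted without adjustment for multiplicity or sequential testing". The final paragraph of Section 9.7.1.6.2 plans an unconditional ANCOVA of "The relationship between clinical changes at 24 months (CDR-SB, ADCOMS, ADAS-cog14, MMSE, and FAQ) and changes in each of the biomarkers".

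The primary objective in Section 8.1 is directional: "To determine whether elenbecestat is superior to placebo on the change from baseline in the Clinical Dementia Rating". The primary alternative in Section 9.7.1.6.1 is not: "The corresponding alternative hypothesis is that there is a difference in the mean change from baseline in CDR-SB at 24 months".

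**The concern.** A testing hierarchy has to restrict which results may be declared significant. It does not have to restrict which effects are estimated, because an estimate with a confidence interval, labelled nominal, spends no alpha. The first sentence goes further and makes carrying out the analysis itself conditional.

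The cost falls mainly on amyloid PET. After a missed primary, the randomised amyloid contrast is what separates two explanations: the drug did not lower brain amyloid, or it did and decline was not slowed. Section 8.2 states the amyloid objective without any condition, and Section 9.1.2.1 has consenting subjects scanned at 12 and 24 months in an optional substudy. Under the rule as written, that objective has no planned analysis when CDR-SB fails. Any estimate then produced would be open to the criticism that it was unplanned, while endpoints ranked below it would have planned comparisons.

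**Working it through.** **1. Is there a planned treatment contrast outside the conditional paragraph?**

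| Endpoint | Where a between-arm comparison is planned | Conditional on the primary? |
|---|---|---|
| Amyloid PET SUVR, pooled and within study | Section 9.7.1.6.2, key secondary paragraphs only | Yes |
| ADCOMS, full population | Section 9.7.1.6.2, key secondary paragraphs only | Yes |
| ADCOMS, SUVR-enriched subset | Section 9.7.1.6.2, other secondary endpoints | No |
| ADAS-cog14, MMSE, FAQ | Section 9.7.1.6.2, other secondary endpoints | No |
| Tau PET, CSF markers, hippocampal volume | Section 9.7.1.7.3 | No |

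Amyloid PET is absent from the biomarker endpoints in Section 9.7.1.1.3 and from the list in Section 9.7.1.7.3. The clinical–biomarker ANCOVA does not fill the gap. It uses amyloid change only as an explanatory variable, so it gives no treatment effect on amyloid. Where ADCOMS change is the response, treatment is a factor but is adjusted for a post-randomisation biomarker change, which is not the randomised ADCOMS contrast. The Extension Phase analyses in Appendix 5 concern subjects who roll over after completing the Core Study, all of whom then receive elenbecestat.

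**2. How often would the condition fail?** Inputs from Section 9.7.2: "group are assumed to be 1.46 and 2.05, respectively, instead of 1.75 and 2.05" (placebo mean change and SD), 25% reduction, 30% dropout, 950 per arm, 90% power, two-sided 0.05.

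The plan's own figure first:

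- Difference: 0.25 × 1.46 = 0.365.
- Evaluable per arm: 2 × (1.960 + 1.282)² × 2.05² / 0.365² ≈ 663.
- Inflated for dropout: 663 / 0.70, rounded up, = 948 per arm, or 1896 in total, against 1900 stated. Reproduced.

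Probability that the primary is not significant (normal approximation):

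- Completers per arm: 950 × 0.70 = 665.
- Standard error: 2.05 × √(2/665) = 0.1124.
- At 25% slowing: 0.365 / 0.1124 = 3.25; power = Φ(3.25 − 1.96) = 0.901 (noncentral t: 0.900); miss = 9.9%.
- At no effect: miss = 95.0%.
- At 15% slowing (an assumed value, not in the protocol): 0.219 / 0.1124 = 1.95; power 0.495; miss = 50.5%.

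These are simply one minus the power of the primary test. They become the probability of having no planned amyloid PET estimate only if the sentence is followed literally.

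**3. What would the repair change?** Estimating in every case leaves alpha, power and sample size as they are. Requiring the primary to be significant in favour of elenbecestat lowers the chance that the sequence starts under no effect from 5.0% to 2.5%. It leaves that chance at 90.1% at the planned effect, because the opposite tail there is about zero.

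**The case against.** The best reply is that one verb is being read too strictly. The sentence that follows describes hypothesis tests in sequence. The next paragraphs say without qualification that ADCOMS and amyloid PET will be analysed by MMRM. The Amendment 05 rationale also speaks of hierarchical testing. Section 9.7.1 plans within-study analyses to confirm trends, and reporting after a stopped sequence is often settled in the SAP, which is not shown. This stands as evidence of intent, and it is why the point is a matter of wording. It does not remove the point: the protocol states a rule rather than leaving one open, the general statement in Section 9.7.1 gives way where something else is specified, and no sentence says estimates will be reported regardless.

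A reader might also infer two stronger things that the documents do not support.

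- *That ADCOMS would go wholly unestimated.* It would not. The SUVR-enriched MMRM is unconditional; only the full-population contrast is affected.
- *That significant harm on CDR-SB would lead to a confirmatory amyloid PET claim.* The test is two-sided ("All statistical tests will be based on the 5% (2-sided) level of significance, unless specified") and the condition names no direction, so harm could literally start the sequence. But the primary and key secondary objectives are worded as superiority, which harm would not meet. ADCOMS comes before PET in the listed order and would also have to be significant, and the probability of reaching PET by that route was not calculated. The nonbinding futility analysis and the DSMB's review of group-level cognitive safety (Section 9.7.3) come earlier. The two-sided fixed sequence keeps familywise error at or below 0.05 in either direction.

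**Conclusion.** The point holds as a defect in wording and prespecification. Taken literally, a non-significant CDR-SB result leaves the Core Study amyloid PET contrast and the full-population ADCOMS contrast without a planned estimate. The primary fails with probability about 10% at the planned 25% slowing and 95% at no effect, assuming 665 completers per arm, a placebo change of 1.46, a common SD of 2.05 and a normal approximation. The consequence rests on the literal reading of the sentence; the surrounding text suggests that the intention was narrower. Primary inference, error control, sample size and data collection are unaffected. The missing direction is a small mismatch with the superiority objectives and should not be presented as a multiplicity error.

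**What to change.** In Section 9.7.1.6.2 and in the synopsis, replace the conditional sentence with:

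> Key secondary endpoints will be analysed, and estimates with 95% CIs reported, whatever the primary result. Confirmatory significance will be claimed only if the primary and every preceding test in the sequence are significant at 2-sided 0.05 in favour of elenbecestat. Results outside the sequence will be labelled nominal.

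The directional phrase aligns the rule with the stated objectives. The cost is one short text change made in two places, with no added subjects, assessments or alpha, and no loss of power at the planned effect.

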9.1.2.1 Treatment Period

During Visit 2, the following assessments will be completed before the subject receives their first dose of study drug: MMSE, CDR, ADAS-cog14, FAQ, and NPI-10. These assessments will provide baseline measurements for the study. For any given subject, every effort should be made to ensure that the CDR rater remains unchanged throughout the study. (revised per Amendment 03) Inclusion and exclusion criteria will be reviewed again together with concomitant medications and assessment of AEs. A single 12-lead ECG will be conducted. All ECG recordings will be evaluated by a central reader. The C-SSRS will also be administered. A baseline routine physical examination with dermatologic review, vital signs measurements, clinical laboratory testing (including viral characterization), urinalysis using urine dipstick, and a urine pregnancy test (females of child-bearing potential only), will be performed. Additional blood samples will be taken for PD/exploratory biomarkers and immunologic assessments. (revised per Amendment 03) Some of the immunologic assessment blood sample will be used to prepare isolated PBMCs which will be stored for testing as needed. (revised per Amendment 02) The results of some of the immunologic assessments will be provided to the DSMB for periodic review during the Core Study. (revised per Amendment 05) Whilst there is no prescribed order in which the assessments at each visit are to be performed, the subject component of the cognitive, functional and quality of life assessments are to be performed in the morning whenever possible, or consistently at the same time of the day and ideally should be completed before the more invasive procedures (eg, physical examination, ECG, blood draw).

Subjects will be randomized at Visit 2 (Day 1) to receive elenbecestat 50 mg per day or placebo administered orally QD in the morning with or without food. Subjects will be encouraged to stay at the site for observation for at least 30 minutes following their first dose of study drug. The duration of this observation period can be extended at the investigator's discretion, eg, if warranted by medical history or concomitant medication (revised per Amendment 03). Double-blinding to study drug will be in effect throughout the Treatment Period.

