9.7.1.2 Definitions of Analysis Sets

- The Randomized Set is the group of subjects who are randomized to study drug.

- The Safety Analysis Set is the group of subjects who receive at least 1 dose of study drug and have at least 1 postdose safety assessment.
- The Full Analysis Set (FAS) is the group of randomized subjects who receive at least 1 dose of study drug and have baseline and at least 1 postdose primary efficacy measurement.
- The Per Protocol Analysis Set (PPS) is the subset of subjects in the FAS who sufficiently comply with the protocol. The PP Analysis Set will be used to conduct a sensitivity analysis of the primary efficacy endpoint. Details of the evaluability criteria will be determined before database lock and treatment unblinding, and will be specified in the statistical analysis plan.
- The PK Analysis Set is the group of subjects with at least 1 quantifiable elenbecestat plasma concentration with a documented dosing history.
- The PD Analysis Set is the group of subjects who have sufficient PD data to derive at least 1 PD parameter.

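### The Cox models for dementia conversion and CDR worsening omit baseline CDR-SB, which every analyzed subject already has; the cost is a modest loss of power, clearest for conversion

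*Protocol*

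**What the plan says.** Section 9.7.1.6.2, repeated in the synopsis under the analyses for other secondary endpoints, specifies the same model for both time-to-event endpoints. They are analyzed on the FAS "using Cox regression model for treatment effect adjusting for randomization stratification factors", and for each "ApoE4 status may be included in the model if appropriate". Section 9.7.1.6.1 lists the stratification factors: "region [7 levels], clinical dementia [yes, no], and concurrent AD medication use at randomization".

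The conversion endpoint is restricted: "Time to conversion to dementia for subjects who were not clinically staged as dementia at Baseline".

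The linear models for CDR-SB are built differently. The primary MMRM contains "baseline CDR-SB, baseline CDR-SB by visit interaction, and randomization stratification variables". For the slope analysis, "The LME model will include treatment group, baseline CDR-SB, randomization stratification variables, assessment time". The multiple-imputation ANCOVA also carries baseline CDR-SB.

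The value is available. Section 9.1.2.1 lists the assessments completed before the first dose at Visit 2: "MMSE, CDR, ADAS-cog14, FAQ, and NPI-10. These assessments will provide baseline measurements for the study". Section 9.7.1.2 defines the FAS as randomized and dosed subjects who "have baseline and at least 1 postdose primary efficacy measurement".

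**The concern.** Both events mark a decline in clinical state, and subjects enter at different distances from it. Inclusion criterion 1 requires a global CDR of 0.5 at Screening, so the global score says little about who starts nearer the next level. Section 9.2.1 describes the global score and the sum of boxes as two summaries of the same six domains, and the sum is the finer one. Section 9.2.3 says the CDR is meant to reflect disease stage. It is therefore reasonable to expect baseline CDR-SB to predict both events, although the protocol gives no estimate of how strongly.

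Leaving a prognostic covariate out of a Cox model pulls the treatment hazard ratio toward 1 and lowers power. Power is what is at stake here, for two endpoints meant to support the CDR-SB result. Because the protocol writes out the covariate set, this is a choice it makes and not a detail left to the SAP.

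**Working it through.** **1. The plan's own sample size reproduces.** Section 9.7.2 gives a placebo change of 1.46, SD 2.05, a 25% reduction, 30% dropout, 90% power and two-sided alpha 0.05.
- Difference: 0.25 × 1.46 = 0.365.
- n per arm = 2 × (1.960 + 1.282)² × 2.05² / 0.365² ≈ 663.
- With dropout: 663 / 0.70 → 948 per arm, 1896 in total, against 1900 stated.
- Power at 950 × 0.70 = 665 per arm: 90.1%.

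The design figures are not in dispute. The protocol gives no power, event count or hazard ratio for the two time-to-event endpoints.

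**2. Severity information left in each model.**

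| Factor | CDR worsening | Dementia conversion |
|---|---|---|
| Region, AD medication | in the model, not severity | in the model, not severity |
| Clinical dementia yes/no | coarse, two levels | constant, so no information |
| ApoE4 (optional) | genotype, not severity | genotype, not severity |
| Baseline CDR-SB | absent | absent |

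With dementia capped at about 25% of subjects (section 9.1), at least about 0.75 × 1900 = 1425 are at risk of conversion.

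**3. What adding a baseline severity covariate gains: proportional-hazards simulation.** The hazard is λ·exp(a·ln HR + x·ln HRsd), where a is treatment and x is standardized baseline severity. λ is set so that 30% or 50% of placebo subjects have the event by 24 months. Dropout is exponential at −ln(0.70)/24 per month, and follow-up ends at 24 months. The treatment HR is 0.75 or 0.80 and N is 1426 or 1900, with 600 runs per setting. Only the 30% dropout, the 24 months, the 1:1 allocation and the total N come from the protocol; event rates, HR and HRsd are assumed. A treatment-only Cox model is compared with treatment plus x.

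| HR per SD of baseline | Change in power over 8 settings (points) |
|---|---|
| 1.0 (not prognostic) | −0.5 to 0.7 |
| 1.3 | −0.2 to 2.9 |
| 1.6 | 0.5 to 6.5 |
| 2.0 | 3.8 to 13.7 |

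The largest gain is at N = 1426, HR 0.80, 50% events and HR 2.0 per SD. Power rises from 66.5% to 80.2%, and the estimated HR is 0.82 without the covariate and 0.80 with it. Monte Carlo standard error for one power near 70% is √(0.7 × 0.3 / 600) = 1.9 points. The comparator contains no strata, so it approximates the conversion model but overstates the gain for CDR worsening.

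**4. Threshold simulation using the CDR-SB inputs.** The slope SD is 1.8 and visit noise 0.98, so √(1.8² + 0.98²) = 2.05. The event is a CDR-SB of at least 4.5 at two consecutive 3-monthly visits. Baseline mean 2.4, baseline SDs 0.7 to 1.3 and the 4.5 threshold are all assumed.
- With no measurement error at baseline and no strata, power rises by 4 to 15 points at n = 1425 (57% to 61%, 50% to 58%, 42% to 57%).
- That is too favorable, because baseline should carry the same error as later visits. With error SD 0.5 or 0.69 and the change SD held at 2.05, the n = 1425 gain is about 0 to 1, 4 to 5 and 6 to 8 points at baseline SD 0.7, 1.0 and 1.3. A repeat with 200 runs per setting gave about 2 to 6 points.
- For CDR worsening at n = 1900, adding a dementia stratum (assumed to be roughly the top 25% of baseline severity) cuts the gain from about 11 to about 4 points at SD 1.0 and from about 16 to about 6 at SD 1.3. The 200-run repeat gave about 1 to 6.

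Monte Carlo error in these runs is a few points.

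**The case against.** The strongest reply is that nothing here is wrong: a Cox model adjusted for the randomization strata is standard and valid. The plan's rule for continuous endpoints is to adjust for the baseline of the response itself. For these events that baseline is either the global CDR, fixed at 0.5 at Screening, or non-dementia status, constant by definition. On that view, borrowing another scale is a preference. Adjustment also yields a conditional hazard ratio, while the companion Kaplan–Meier estimate for conversion is marginal.

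Much of this stands. The issue is efficiency only, and the change of estimand has to be stated. It does not remove the point, because a response baseline that is nearly constant is exactly where a finer severity measure has something to add.

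Three stronger readings are tempting and not supported. A reader might infer that neither model carries any severity adjustment; the CDR-worsening model does, through the dementia stratum. A reader might infer bias or an inflated type I error; neither follows. A reader might infer a double-digit power loss; such figures need a strongly prognostic baseline, or a comparator without strata and a baseline free of error. The 4.5 threshold is also not the protocol's event: section 9.7.1.1.2 illustrates CDR worsening by the global score, and conversion is a centrally reviewed clinical staging with no two-visit confirmation.

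**Conclusion.** The point holds as a modest, nearly free improvement. In the conversion analysis no baseline severity covariate remains. In the CDR-worsening analysis a coarse one does, so less is gained. The likely cost of the omission is roughly 0 to 6 points of power, with slight attenuation of the hazard ratio, if baseline CDR-SB is moderately prognostic. It is more only if the covariate is strongly prognostic, and about zero if it is not prognostic. These figures rest on assumed event rates, hazard ratios, baseline spread and prognostic strength, so the direction is firmer than the size. Both endpoints are other secondary endpoints outside the sequential testing procedure, so the primary and key secondary conclusions are untouched.

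**What to change.** In section 9.7.1.6.2 and the matching synopsis text, add continuous baseline CDR-SB as a prespecified covariate in both Cox models and state that the hazard ratio is conditional on it. Do this before unblinding, since adding it later would be post hoc. Omitting the constant dementia factor from the conversion model is tidying only. Section 9.7.1.6.3 analyzes time to change of AD treatment in the same way as conversion, so say whether the covariate carries over.

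The cost is one phrase in each place and one model parameter. No new data are needed and no FAS subject is lost.
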